Data will be summarized by group and in total. In summary tables of continuous variables, we will report the range, mean, and standard deviation. We will also inspect the median and semi-interquartile range and report as needed. We will use counts and percentages in tables for categorical variables. The denominator for each percentage will be the number of participants within the group unless otherwise specified. Hypothesis testing will be carried out at a two-tailed Type I error rate of $\alpha = .05$ (e.g., for comparing full to reduced regression models), and/or corresponding 95% confidence intervals (e.g., for interpretation of regression coefficients) unless otherwise specified. If statistical methods change during analysis (e.g., non-normality of residuals, heteroscedasticity), the changes will be documented in the write-up of the results along with justification. Additional analyses of these data will be inevitable, but any exploratory analyses will be clearly marked as such.

Statistical power analysis and sample size selection

In planning the DRIVEN trial, various scenarios around different effect sizes, sample sizes, drop-out rates, and variance estimates were considered. For the possibility of finding a job as an outcome, we used *powerSurvEpi* in R^{1,2} to estimate power for proportional hazard models under different conditions of sample size, hazard ratios, and probability of job-finding. With a 10% difference between groups (e.g., 35% vs 45% chance of finding a job) power is 80% with the proposed $N = 50$ per group (total $N = 100$, although 126 will be recruited to account for 20% up to attrition). Effects smaller than 10% would not be clinically/practically meaningful, and we would be underpowered for these smaller effect sizes. For continuous outcomes, we conducted Monte Carlo simulations following guidance from the clinical trial literature and we included longitudinal assessments each week to achieve a "longer", and thus more powerful, data set. We assumed a Type I error rate of .05 and based effect-size and variance estimates on previous research.^{2,3} Simulations indicated that power for the time \times DRIVEN interaction would be 94% even for medium-sized effects (treatment effect = 0.7), and assuming a drop-out rate of 20%. We examined power for a variety of simulated conditions (e.g., sample size, effect size), which led us to

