an overall sample size of $N = 126$ overall. Power for simple between-group comparisons of continuous outcomes (e.g., job search behavior) was also examined in the *pwr* package of R; these analyses showed 98% power for the DRIVEN vs. self-guided job-seeking group comparison with large effects ($d = 0.8$), and 93% power for smaller effects ($d = 0.7$).

We also planned some auto-regressive analyses, which we anticipate will have high power owing to the large number of repeated measures in the design; power was approximated by considering the number of t and $t + 1$ observations available for associations. Considering all data points (~100 participants times 22 weeks with a prior week available as a predictor), effect sizes as small as $r = .1$ would be detectable (calculations done in *pwr* package), even when missing data were estimated as much as 50% (i.e., half of weeks left incomplete).

We acknowledge that some changes were made to our design after the power analyses were completed (e.g., there are 6 weeks of survey outcomes plus 2 follow ups), but we deemed these changes necessary on practical grounds (e.g., to reduce participant burden) and did not recalculate power. These changes should not imperil statistical power because we have refined our approach to use a simpler model with fewer parameters (i.e., polynomial regression of continuous time, and time \times treatment interaction).

Missing data and outliers

We will approach the analyses from an intent-to-treat perspective. All participants will be included in the mixed modelling, which can be accommodated using the *nlme* package of R. Although we will inspect the data for outliers and influence, we do not plan to drop cases.

Study Timepoints

There is a baseline assessment, six weeks of intervention with weekly surveys, and two follow-up assessments. The baseline assessment will be included as a covariate and not included as part of the outcome. Time will be treated as a continuous variable calculated as “days since baseline”. The mixed effects modelling will include all observations of the Job Search Behavior questionnaire starting from baseline out to the 16-week post-intervention assessment.

The purpose of the two follow-up assessments (8 and 16 weeks) is to (a) provide a period of time for the person to possibly find a job and (b) examine the trajectory of change in the two groups in job search behavior, from during the acute intervention into a 16-week follow-up period.

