Interim analyses to ensure data quality

In order to ensure data integrity and quality, we will conduct limited interim data analyses. The goal of this analysis will be to conduct a “dry run” of data management procedures. We will import these data from REDCap and inspect them for data quality, and to test scoring algorithms for questionnaires. In these interim analyses, some preliminary results may be shared with potential investors and/or sponsors of the DRIVEN program, but these analyses will not be submitted for publication. The definitive analyses of the RCT will be as described below.

Primary analyses

Job Search Behavior: Preparatory and Active Job Searching

Because the surveillance period of this study may be too short to evaluate whether the participants found jobs

or not, the primary outcome measure will be the Job Search Behavior questionnaire, which has two separate subscales for preparatory versus active job searching. We will use a mixed model with random intercepts for each participant, using the maximum likelihood estimator. Time will be included as a continuous variable as described above (i.e., days since baseline). Because baseline is included as a covariate and not part of the outcome, we will include both a main effect of treatment as well as interaction effects with time. We will then fit a corresponding model with no effects of treatment. Treatment will be coded as Control = 0; DRIVEN = 1. In this way, the effect of treatment can be evaluated by comparing the full to the reduced model. In R pseudocode, the model will appear as follows:

```

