# Note: Using this R syntax, main effects are also included
# (i.e., tx, t, and t2).
full_model <- lme(jsb ~ tx * t + tx * t2, random = ~1 | id, data = data)
reduced_model <- lme(jsb ~ t + t2, random = ~1 | id, data = data)
```

Alternative approaches and model modifications

Although we hypothesize the models above, it is possible that data-driven modifications will be needed to the model. These include:

- Consideration of an alternative estimator (e.g., REML) and/or bootstrapped confidence intervals
- The possibility the model could be substantially improved by including cubic, etc., effects
- The possibility of random slopes in addition to random intercepts

We have chosen to focus on a simpler model to ease interpretation and to avoid overfitting, but we will adjust the model as needed based on inspection of the results and diagnostics (e.g., inspection of residuals for normality, heteroscedasticity, influential observations).

Mediation analyses to evaluate mechanism

We envision that participants' job seeking will improve as their emotional distress improves, and vice versa. In other words, we hypothesize a bidirectional relationship between job seeking and depression. We will evaluate this using a random-intercept cross-lagged panel⁴ model in *lavaan* in R, using the `missing = "ML"` argument for missing data that allows for ML estimates for missing-at-random data. Each time point will be regressed on the previous time point. Slopes that are equally spaced in time will be constrained to be equal as a means to lower the number of parameters estimated. Because the purpose of this analysis is to evaluate the mechanism of DRIVEN, we will only conduct it in the DRIVEN group. The main outcomes of this analysis will be the magnitude of the cross-lagged regressions – job searching predicting depression, and depression predicting job searching.

Secondary analyses

Analyses of secondary continuous outcomes, and other exploratory analyses, will be done using mixed models, using the same approach as described above.

Because an important secondary outcome is whether the person obtained a job or not, we will also time-to-event analyses (a.k.a., survival analyses) to create hazard curves of "time unemployed". The primary variable of interest will be treatment group, but other exploratory covariates may be added to the model (e.g., do people with higher baseline depression spend more time in unemployment?).

REFERENCES CITED

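### The promise that all participants enter the mixed model conflicts with the stated role of baseline, and the primary analysis has no stated missing-data assumption and no dropout sensitivity analysis

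*SAP*

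**What the plan says.** - *Missing data and outliers*: "We will approach the analyses from an intent-to-treat perspective. All participants will be included in the mixed modelling". The SAP adds that the nlme package can accommodate this and that outlying cases will not be dropped. The section names no missing-data mechanism, no rule for people without post-baseline data, and no sensitivity analysis.
- *Study Timepoints*: "The baseline assessment will be included as a covariate and not included as part of the outcome". Two sentences later: "The mixed effects modelling will include all observations of the Job Search Behavior questionnaire starting from baseline out to the 16-week post-intervention assessment".
- *Primary analyses*: "We will use a mixed model with random intercepts for each participant, using the maximum likelihood estimator". The section then begins a sentence with "Because baseline is included as a covariate and not part of the outcome" and gives this as the reason for including a main effect of treatment.
- Model code: "full_model <- lme(jsb ~ tx * t + tx * t2, random = ~1 | id, data = data". Neither the full nor the reduced model has a baseline term.
- *Mediation analyses to evaluate mechanism*: the software option is described as an "argument for missing data that allows for ML estimates for missing-at-random data". This is the only mention of missing at random. It concerns the cross-lagged panel model, which is fitted in the DRIVEN group alone.
- *Statistical power analysis and sample size selection*: 126 are to be recruited to allow for up to 20% attrition, and the longitudinal simulations were run "assuming a drop-out rate of 20" per cent with a treatment effect of 0.7.
- *Alternative approaches and model modifications*: the list covers the estimator, bootstrapped intervals, higher-order time terms and random slopes. It has nothing on dropout.

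**The concern.** There are two separate gaps.

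The first is who is analysed. A mixed model uses every participant who has at least one outcome value. If baseline is only a covariate, a person who withdraws before the first weekly survey has no outcome value and contributes nothing. The inclusion sentence is then untrue for that person.

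The second is what the model assumes about people who leave later. Maximum likelihood with a random intercept implicitly predicts unseen scores from the arm's time curve and the person's own level. This is sound if, given arm, time, baseline (if included) and the observed job-search scores, the unseen scores do not depend on having dropped out. It is not sound if dropouts lose benefit in a way that their earlier scores do not show.

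The trial gives some reason to ask. *Study Background* links distress to poorer job-search activity, and the mediation section hypothesises that depression and job seeking influence each other, yet depression is not in the primary model. The arms also differ in contact: coaching, activities and an app against a weekly e-mail. One stated purpose of the follow-ups is to compare trajectories after the intervention, which is where missing data would accumulate. The plan offers nothing that would show a reader whether the primary conclusion depends on the assumption.

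**Working it through.** **1. The plan's own figures.** 50 / (1 − 0.20) = 62.5, rounded up to 63 per arm, gives 126. Power of a two-sample t-test with 50 per arm at two-sided 0.05 is 97.7% for d = 0.8 and 93.4% for d = 0.7, against 98% and 93% in the SAP. These reproduce. The 20% and the 0.7 are therefore used below as the plan's own planning values, with 0.7 read as SD units (an assumption).

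**2. Who has an outcome row.**

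| Statement | Person with baseline only |
|---|---|
| Missing data: everyone is in the mixed model | included |
| Study Timepoints: baseline is a covariate only | no outcome row, not included |
| Primary analyses: the same, and the reason for the treatment main effect | no outcome row, not included |
| Study Timepoints: observations run from baseline | has an outcome row, included |
| Model code | no baseline covariate; does not settle it |

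The SAP does not give the share with no post-baseline survey. At an assumed 5%, 126 × 0.05 = 6.3, leaving about 120. At 10%, 126 × 0.10 = 12.6, leaving about 113.

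**3. Later dropout, by arithmetic.** Let r be the share of benefit that DRIVEN dropouts keep. The effect in everyone randomised is 0.7 × [1 − 0.20 × (1 − r)]. A model that continues dropouts along their arm's curve aims at 0.7.

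- r = 1: 0.70, no overstatement.
- r = 0.5: 0.7 × 0.90 = 0.63; 0.07 / 0.63 = 11%.
- r = 0: 0.7 × 0.80 = 0.56; 0.14 / 0.56 = 25%.

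**4. Later dropout, by simulation.** The stated model plus baseline as covariate was fitted by maximum likelihood to 200 simulated trials per scenario with 63 per arm. Assumptions: about half the variance is between persons; the effect rises to 0.7 SD by week 6 and then stays level; dropout is 20% in each arm, with timing spread evenly over visits; scores do not fall before dropout; benefit is fully lost afterwards. The true effect at the last visit is 0.56.

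- Follow-ups at weeks 8 and 16 from baseline: estimates 0.68 to 0.70.
- Follow-ups 8 and 16 weeks after the intervention (weeks 14 and 22): estimates 0.64 to 0.67, an excess of 14% (0.64 / 0.56) to 20% (0.67 / 0.56). Here the quadratic curve alone gives about 0.66 with no dropout.

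At either timing, the estimate barely changes when dropout is introduced. This confirms that the model projects dropouts along their arm's curve.

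**5. Unequal dropout.** Assume 10% in one arm and 30% in the other, with dropouts 0.5 SD below the model's prediction. The bias in the arm difference is 0.5 × (0.30 − 0.10) = 0.10 SD. It favours DRIVEN if DRIVEN loses 30%, and goes against DRIVEN if the comparison arm does.

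**The case against.** The strongest reply is that the inclusion sentence is true if baseline is an outcome row, as one *Study Timepoints* sentence suggests. That reading is available, but it contradicts two explicit statements and removes the reason that the SAP gives for the treatment main effect. It is a contradiction to resolve and does not answer the point. Nor would it help with later dropout, because a baseline score says nothing about what happened afterwards. On either reading, anyone with one weekly survey stays in.

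A reader might infer that the plan will inflate DRIVEN's effect by a quarter. The SAP does not support that:

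- It does not say that people who stop coaching also stop answering surveys. If they keep answering, their scores enter the model.
- Coaching lasts six weeks. Someone who completes it and then misses a follow-up has not left coaching and may keep the benefit.
- The 20% is an upper planning figure, and 25% needs every dropout to lose all benefit with no warning in earlier scores.
- The direction is open. Participants who find a job may stop searching, and heavier loss in the e-mail arm could understate the effect.
- That leaving depends on depression is plausible, but the SAP does not say so.

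The primary test also compares full and reduced models jointly across visits, and loss of benefit alone cannot create an effect where none exists. That limits the threat mainly to the size of the effect late in follow-up. Unequal dropout is different, since its bias needs no true treatment effect.

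All of this stands as a limit on size and direction. It does not supply the missing assumption or the missing check.

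**Conclusion.** The point holds in a limited form. The SAP contradicts itself on whether baseline is an outcome. Under the version that it states twice, its inclusion claim fails for participants with no post-baseline survey; how many that will be is unknown. The primary analysis also rests on an unstated missing-at-random assumption and has no analysis that tests it or is certain to cover all 126 randomised.

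The size depends on assumptions that the SAP does not give. With 20% dropout and a 0.7 SD effect, the possible overstatement at follow-up runs from 0 to about 25%, with about 11% if half the benefit is kept. Unequal dropout could move the estimate by about 0.10 SD in either direction in the example above. These are illustrations of sensitivity, not forecasts of bias. They do not show that the mixed model is the wrong primary analysis, and it need not be replaced.

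**What to change.** 1. Reconcile the two *Study Timepoints* sentences, the *Primary analyses* text and the model code. If baseline is a covariate, add it to both models and say that the primary model uses participants with at least one post-baseline survey. If baseline is to be an outcome row, say so and revise the reason given for the treatment main effect.
2. State that the primary model assumes missing at random given arm, time, baseline (if included) and observed job-search scores.
3. Pre-specify one sensitivity analysis in all 126 randomised: multiple imputation using baseline and observed job search plus the depression and employment data that the trial already collects as secondary outcomes, followed by a reference-based or delta-adjusted (tipping-point) version. Keep the imputation model small, given about 63 per arm. Report how far the primary conclusion depends on the assumption. Control-based imputation should not be the only test of robustness, because it may not fit people who completed the program.

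The cost is a few sentences of SAP text and one further analysis, with no new data collection. The downsides are that a rich imputation model could be unstable at this sample size and that the sensitivity estimate may be smaller than the primary one. The choice should be fixed before outcome results are seen, because a sensitivity analysis chosen afterwards is less credible.

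### The SAP contradicts itself on whether baseline scores are outcome rows in the primary mixed model; if they are kept, an early sustained benefit is reported with the wrong shape

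*SAP*

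**What the plan says.** Study Timepoints gives two rules. The first is "The baseline assessment will be included as a covariate and not included as part of the outcome". Two sentences later comes the second: "The mixed effects modelling will include all observations of the Job Search Behavior questionnaire starting from baseline out to the 16-week post-intervention assessment".

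The primary analysis section sides with the first rule and rests the model's form on it: "Because baseline is included as a covariate and not part of the outcome, we will include both a main effect of treatment as well as" interactions with time. It specifies the estimator ("We will use a mixed model with random intercepts for each participant, using the maximum likelihood estimator") and the test: "the effect of treatment can be evaluated by comparing the full to the reduced model".

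The code that follows is "full_model <- lme(jsb ~ tx * t + tx * t2, random = ~1 | id, data = data" and "reduced_model <- lme(jsb ~ t + t2, random = ~1 | id, data = data". It has no filter on time and no baseline term. The Secondary analyses section carries the same approach over to the secondary continuous outcomes.

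**The concern.** The two sentences lead to different data sets. Under the first rule, the day-0 score appears only on the right-hand side. Under the second, each participant also contributes a day-0 outcome row, and if the covariate is added as the text intends, that row is predicted from itself.

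Randomisation makes the expected arm difference zero at day 0. If the intervention has an effect by week 1 that then persists, the true difference jumps between day 0 and day 7. A quadratic in days cannot follow a jump. It compromises by starting too low, overshooting later and bending down at the end.

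The SAP says the follow-ups serve partly to describe how the two arms evolve from the intervention period into follow-up, and it reports power for the time-by-treatment interaction. The quantity at risk is therefore one the trial means to interpret. A steady benefit could be written up as one that builds, peaks at the first follow-up and fades.

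**Working it through.** **Inputs from the SAP.** 50 analysable participants per arm; baseline, six weekly surveys and two follow-ups; random intercept; quadratic time; two-sided 0.05.

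**Assumptions.** Complete data; total SD 1; intraclass correlation (ICC) 0.5, range 0.3 to 0.7; weekly surveys at days 7 to 42. Follow-ups at days 98 and 154 if the 8 and 16 weeks run from the end of the intervention (42 + 56, 42 + 112), or days 56 and 112 if they run from baseline.

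**The plan's own figure.** A two-sample t test with 50 per arm has noncentrality d × √(50/2): 4.0 at d = 0.8 and 3.5 at d = 0.7. Power is 97.7% and 93.4%, matching the stated 98% and 93%. No figure in the plan is disputed here.

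**Step 1: fitted shape.** With complete, balanced data and a random intercept, the expected fitted arm difference is the least-squares quadratic a + bt + ct² through the true differences, whatever the ICC. Take the truth as 0 at day 0 and 1 at each later visit.

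Day-0 row kept, follow-ups at days 98 and 154: a = 0.5866, b = 0.01433, c = −0.00007934.
- Day 7: 0.5866 + 0.1003 − 0.0039 = 0.68
- Day 42: 0.5866 + 0.6019 − 0.1400 = 1.05
- Day 98: 0.5866 + 1.4044 − 0.7620 = 1.23
- Day 154: 0.5866 + 2.2069 − 1.8816 = 0.91

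With follow-ups at days 56 and 112, the values at week 1, week 6 and the two follow-ups are 0.64, 1.10, 1.18 and 0.95.

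Day-0 row dropped: a = 1, b = c = 0, so 1.00 at every visit.

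**Step 2: the 2-df time-by-treatment test.** Noncentrality = d² × (50/2)/(1 − ICC) × S, where S is the sum of squared deviations of the nine fitted values from their mean. For days 98 and 154, S = 0.302. At d = 0.5:
- ICC 0.5: 0.25 × 25/0.5 × 0.302 = 3.78, rejection 39.5%
- ICC 0.7: 0.25 × 25/0.3 × 0.302 = 6.30, rejection 60.6%

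With days 56 and 112 the figures are 48% and 71%. Simulation with likelihood-ratio tests agrees for days 98 and 154 (39% at ICC 0.5; 58% to 60% at 0.7). With the rows dropped, rejection is about 5%.

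**Step 3: no treatment effect.** In 1,000 simulated trials at ICC 0.5, the interaction test rejects in 5.0% with the rows in and 5.1% with them out. The 3-df full-versus-reduced test rejects in 5.8% to 6.3% against 5.4% to 5.6%. A larger check (9,000 trials at each of ICC 0.5 and 0.7, baseline as covariate) gives 6.0% to 6.1% against 5.4%.

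**Step 4: power of the 3-df test at d = 0.5.** With baseline as covariate: 97% at ICC 0.5 and 99% at 0.7, rows in or out. With the code as written (no covariate), dropping the rows lowers power from about 85–87% to 80–82% at ICC 0.5, and from 87% to about 67–69% at 0.7.

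**Step 5: other shapes** (days 98 and 154, as multiples of the plateau).

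| Benefit | Visit | Truth | Rows in | Rows out |
|---|---|---|---|---|
| Six-week ramp, then flat | Week 1 | 0.17 | 0.22 | 0.26 |
| | Week 6 | 1.00 | 0.83 | 0.82 |
| | Day 98 | 1.00 | 1.23 | 1.20 |
| | Day 154 | 1.00 | 0.93 | 0.94 |
| Three-week ramp, then flat | Day 98 | 1.00 | 1.32 | 1.20 |

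A benefit growing linearly from day 0 is recovered exactly with the rows in or out.

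**The case against.** The strongest reply is that the SAP has largely answered the question. It says twice that baseline is not an outcome, and the primary analysis section reasons from that. The sentence at issue follows the definition of time as days since baseline and may only describe the time span. A careful analyst would probably settle it correctly. That is fair, and it makes this a wording conflict rather than a wrong analysis deliberately chosen. But nothing in the SAP says that the sentence is only descriptive, and the code does not break the tie.

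It is also fair that a full benefit by day 7 that then stays flat is close to the worst case for a six-week programme. Under a six-week ramp, the peak-then-fade shape appears with or without the day-0 rows, because the quadratic itself produces it. This limits the size of the concern, and the percentages for the flat case should not be quoted without that condition.

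A reader might go further and infer that keeping baseline rows manufactures a treatment effect, or an interaction, when the intervention does nothing, or that the Type I error of the primary comparison is compromised. The calculations do not support this. With no effect the interaction test stays near 5%, and the 3-df test moves by only about half a point to one point. Nor is the fitted day-0 difference forced to zero: it is attenuated to 0.59 of the true effect (0.51 with follow-ups at days 56 and 112).

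**Conclusion.** The contradiction is real, concerns the primary model and should be removed before analysis. Its consequence is conditional. If day-0 rows are kept and treatment has an early, sustained benefit, the estimated trajectory is about a third too low at week 1 and about a fifth too high at the first follow-up, and a flat post-baseline effect is often declared to vary with time. If the benefit builds gradually over the six weeks or grows linearly, the rows make little or no difference. The overall treatment verdict barely changes once baseline is a covariate. The sizes rest on assumed ICCs, visit days, complete data and a constant benefit from week 1, none of which the SAP fixes.

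**What to change.** Replace the conflicting sentence in Study Timepoints with: *The outcome in the mixed models is every post-baseline Job Search Behavior score, from the week 1 survey through the 16-week follow-up; the baseline score enters only as a covariate.*

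Filter the data to `t > 0` before both model calls, and put the baseline score in both:
- full: `jsb ~ jsb_baseline + tx*t + tx*t2`
- reduced: `jsb ~ jsb_baseline + t + t2`

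Make the two code changes together. Filtering without the covariate discards the baseline information and costs the power shown in step 4 of the working.

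The cost is one sentence, one filter and one model term. The one downside is that a participant with no post-baseline score contributes no outcome row. The statement under Missing data and outliers that every participant enters the mixed modelling should therefore be reworded to all randomised participants with at least one post-baseline score.
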